5.1.3 Exploratory Endpoints

- Time to OS: defined as the time from first dose of study drug until the date of death from any cause. Subjects who are lost to follow-up and those who are alive at the date of data cutoff will be censored at the date the subject was last known to be alive (or the data cutoff date).
- PFS-4 in Cohort 3A (see SAP [Section 7.1](#)).

5.2 Study Subjects

5.2.1 Definitions of Analysis Sets

The following analysis sets will be defined:

- **Full Analysis Set** includes all enrolled subjects who have not failed study screening. Demographic and baseline characteristics, previous anticancer medications, prior and concomitant medications, procedures and radiotherapy, medical history, and efficacy analyses will primarily be based on the Full Analysis Set.
- **Per Protocol Analysis Set** includes those subjects who (1) receive at least 1 dose of the assigned study drug; (2) have no major protocol deviations; (3) had both Baseline and at least 1 postbaseline tumor assessment. This will be the secondary analysis set for all tumor response-related efficacy endpoints.
- **Safety Analysis Set** includes all subjects who received study drug. This will be the analysis set for all safety evaluations.
- **Palatability Analysis Set** includes all subjects who received oral suspension of lenvatinib and answered at least 1 question in the Palatability Questionnaire CRF.
- **Pharmacokinetic (PK) Analysis Set** includes all subjects who have received at least 1 dose of any study drug and have evaluable lenvatinib concentration data.

This additional analysis set will be defined for Cohort 1:

- **DLT Analysis Set** includes all subjects who either a) experience DLT during Run-in Period or Cycle 1 or b) receive all scheduled doses of study drug on their scheduled days during Cycle 1 and complete Cycle 1 observation period without a DLT.

This additional analysis set will be defined for Cohort 3A:

- **DLT Analysis Set** includes all subjects who either a) experience DLT during Cycle 1 or b) receive all scheduled doses of study drug on their scheduled days during Cycle 1 and complete Cycle 1 observation period without a DLT.

See [Section 7.2](#) explaining the analysis sets in addition to those listed in the protocol.

The number and percentage of subjects included in each analysis set will be presented by cohort and dose level in Phase 1 and by cohort in Phase 2. A listing will also be provided to identify subjects in each analysis set.

5.2.2 Subject Disposition

The number and percentage of enrolled and treated subjects who completed study drug and who discontinued study drug will be summarized according to the primary reason for discontinuation by cohort and dose level in Phase 1 and by cohort in Phase 2. Additionally,

the disposition of subjects who discontinued treatment or withdrew from the study will be summarized. For Cohorts 3A and 3B (combination therapy), reasons for prematurely discontinuing either lenvatinib or chemotherapy (etoposide + ifosfamide) will be summarized separately.

5.2.3 Protocol Deviations

All major protocol deviations will be determined and will be agreed upon after review of individual subject data prior to database lock. This review will be undertaken in collaboration between the Study Director, the Study Statistician, the Study Data Manager and the Study Clinical Operations Manager.

Major protocol deviations will be listed and summarized by cohort and dose level in Phase 1 and by cohort in Phase 2.

5.2.4 Demographic and Other Baseline Characteristics

Demographic and baseline characteristics for the Full Analysis Set will be summarized by cohort using descriptive statistics. Continuous demographic and baseline variables including age (year), height (cm), weight (kg), BMI (kg/m^2) and BSA (m^2), results will be summarized and presented as n, mean, standard deviation, median, Q1, Q3, minimum and maximum values. For categorical variables, the number and percentage of subjects will be used.

Demographics and Baseline categorical variables include age group (2 to <6 years, 6 to <18 years, 6 to <12 years, 12 to <16 years, 16 to <18 years, 18 to ≤ 25 years [Cohorts 2B, 3A and 3B only]), race (White, Black or African American, Asian [Japanese, Chinese, Other Asian], American Indian or Alaska Native, Native Hawaiian or other Pacific Islander, and Other), ethnicity (Hispanic or Latino, not Hispanic or Latino), pregnancy test (present, absent), KPS or Lansky play scores.

Previous anticancer therapy will be summarized by cohort and dose level in Phase 1 and by cohort in Phase 2 as follows:

- Number of previous therapy regimens
- Duration of last medication (months)
- Best response for last anticancer medication (CR, PR, SD, PD, not evaluable, not applicable, unknown)
- Time from end of last anticancer medication to first dose of study drug (months)
- Previous anticancer medication (administered as adjuvant, therapeutic, neoadjuvant, consolidation, maintenance, unknown)
- Previous anticancer procedures (yes, no)
- Time from prior anticancer procedures to first dose (months)
- Prior anticancer medication preferred term

Previous anti-VEGF/VEGFR (vascular endothelial growth factor/vascular endothelial growth factor receptor) therapy will be summarized by cohort and dose level in Phase 1 and by cohort in Phase 2 as follows:

- Number of subjects with any previous VEGF/VEGFR-targeted therapy
- Previous VEGF/VEGFR-targeted therapy (sunitinib, pazopanib, etc.)
- Duration of most recent VEGF/VEGFR-targeted therapy (months)
- Primary reason for discontinuation
- Time from end of most recent VEGF/VEGFR-targeted therapy to first dose of study drug

Prior radiotherapy and radioiodine therapies will be summarized by cohort and dose level in Phase 1 and by cohort in Phase 2 as follows:

- Subjects with any previous radiotherapy
- Tumor lesion at the site progressed since radiotherapy (yes, no, not evaluated)
- Time from last radiotherapy to first dose (months)
- Number of subjects with any previous radioiodine therapy
- Time from last radioiodine therapy to first dose (months)
- Type of previous radioiodine therapy (curative, palliative or other)

Disease history and characteristics at study entry will be summarized by cohort and dose level in Phase 1 and by cohort in Phase 2 as follows:

- Solid tumor diagnosis classification
- DTC subtype classification (papillary, follicular) and histologic subtypes (Cohort 2A only)
- Time since first diagnosis of solid tumor/DTC/osteosarcoma to date of first dose (months)
- Time since metastatic diagnosis to date of the first dose (months)
- Time Since Last Progression to First Dose of Study Drug (months)
- Age at diagnosis (in years)
- TNM staging and grade at diagnosis
- Target lesions (lymph node [yes/no], nonlymph node [yes/no]), and nontarget lesions [yes/no] based on the measurable disease criteria at study entry (nonlymph node: longest diameter ≥ 1.5 cm, lymph-node: short axis diameter ≥ 1.0 cm) based on RECIST version 1.1.

Previous anticancer therapies, anti-VEGF/VEGFR therapy, radiotherapy and radioiodine therapies, and disease history and characteristics at study entry will also be listed for each subject.

A subject data listing of medical history will be provided, including system organ class; current medical condition; date of diagnosis, surgical procedure, or onset of symptoms; and end date/ongoing. Coding will be done using the Medical Dictionary for Regulatory Activities (MedDRA) version 21.1.

Some items captured on the Previous Anti-Cancer Procedures CRF for Cohorts 1 and 2B are excluded from the summary table of Previous Anti-Cancer Procedures because they are diagnostic procedures considered as Medical History and Current Medical Conditions. These items will be flagged in the listing of Previous Anti-Cancer Procedures.

5.2.5 Prior and Concomitant Therapy

All investigator terms for medications recorded on the CRF will be coded using the World Health Organization (WHO) Drug Dictionary using the 2018 B2 version. The number (percentage) of subjects who have taken prior and concomitant medications will be summarized on the Full Analysis Set, by Anatomical Therapeutic Chemical (ATC) Classification, WHO drug preferred term, and by cohort. Prior medications will be defined as medications that started prior to the first dose of study drug and discontinued prior to the start of study drug. Concomitant medications will be defined as medications that (i) have started before the first dose of study drug and are continuing at the time of the first dose of study drug, or (ii) have started on or after the date of the first dose of study drug up to 30 days following the last dose. Medications that cannot be determined to be prior/concomitant due to missing or incomplete dates will be regarded as concomitant (see [Section 5.3.5.2](#)).

The summary of prior and concomitant antihypertensive, antidiarrheal and other medications will be summarized by cohort and dose level in Phase 1 and by cohort in Phase 2. Data listings will be provided for all prior and concomitant medications.

All other concomitant therapies or diagnostic, therapeutic, or anticancer procedures relating to malignancy, and palliative radiotherapy will also be summarized and/or listed as applicable.

5.2.6 Treatment Compliance

Not collected on CRF.

5.3 Data Analysis General Considerations

For incomplete dates involving efficacy and other safety data, a conservative imputation will be used for calculation. See [Section 8.2.1](#) for the outline of imputation rules, which will be specified in the study analysis dataset specifications with more details.

5.3.1 Pooling of Centers

Subject data from all centers will be pooled for all analyses. Center will not be considered as a factor in the analyses.

5.3.2 Adjustments for Covariates

No adjustment for covariates will be made for this study.

5.3.3 Multiple Comparisons/Multiplicity

No multiplicity adjustment will be made for this study.

5.3.4 Examination of Subgroups

Subgroup analyses may be conducted if appropriate.

5.3.5 Handling of Missing Data, Dropouts, and Outliers

5.3.5.1 Adverse Events

Adverse events with incomplete start dates will be considered treatment emergent if:

- Day and month are missing and the year is equal to or after the year of the first study drug dose date
- Day is missing, and the year is after the year of the first study drug dose
- Day is missing and the year is equal to the year of the first study drug dose date and the month is equal to or after the month of the first dose date
- Year is missing; or complete date is missing

5.3.5.2 Concomitant Medications

Medications will be considered concomitant if:

- Day and month are missing and the year is equal to or after the year of the first study drug dose date
- Day is missing, and the year is after the year of the first study drug dose
- Day is missing and the year is equal to the year of the first dose date and the month is equal to or after the month of the first study drug dose date
- Year is missing; or complete date is missing

5.3.6 Other Considerations

Subjects in Cohort 1 will be assigned to the planned dose levels of 9 mg/m^2 , 11 mg/m^2 , 14 mg/m^2 , and 17 mg/m^2 , respectively. The actual dose level could be different from the planned dose level due to the adjustment of BSA and capped dose. The actual dose level resulting from capping the dose will be set as:

- 17 mg/m^2 , if the rounded calculated dose level on Cycle 1 Day 1 $\geq 17 \text{ mg/m}^2$
- 14 mg/m^2 , if $14 \text{ mg/m}^2 \leq$ the rounded calculated dose level on Cycle 1 Day 1 $< 17 \text{ mg/m}^2$
- 11 mg/m^2 , if $11 \text{ mg/m}^2 \leq$ the rounded calculated dose level on Cycle 1 Day 1 $< 14 \text{ mg/m}^2$
- 9 mg/m^2 , if $9 \text{ mg/m}^2 \leq$ the rounded calculated dose level on Cycle 1 Day 1 $< 11 \text{ mg/m}^2$
- 7 mg/m^2 , if $7 \text{ mg/m}^2 \leq$ the rounded calculated dose level on Cycle 1 Day 1 $< 9 \text{ mg/m}^2$
- 5 mg/m^2 , if the rounded calculated dose level on Cycle 1 Day 1 $< 7 \text{ mg/m}^2$

Subjects in Cohort 3A (Combination Dose-Finding) will receive study drug as described in Table 2 of the Protocol. The actual dose level of lenvatinib could be different from the planned dose level due to the adjustment of BSA and capped dose. The actual dose level of lenvatinib resulted from capping the dose will be set as:

- 14 mg/m^2 , if the rounded calculated dose level on Cycle 1 Day 1 $\geq 14 \text{ mg/m}^2$
- 11 mg/m^2 , if $11 \text{ mg/m}^2 \leq$ the rounded calculated dose level on Cycle 1 Day 1 $< 14 \text{ mg/m}^2$
- 9 mg/m^2 , if $9 \text{ mg/m}^2 \leq$ the rounded calculated dose level on Cycle 1 Day 1 $< 11 \text{ mg/m}^2$
- 7 mg/m^2 , if $7 \text{ mg/m}^2 \leq$ the rounded calculated dose level on Cycle 1 Day 1 $< 9 \text{ mg/m}^2$
- 5 mg/m^2 , if the rounded calculated dose level on Cycle 1 Day 1 $< 7 \text{ mg/m}^2$

The actual dose level of ifosfamide and etoposide that resulted from a BSA adjustment will be set as:

Ifosfamide:

- 3000 mg/m^2 if the calculated dose level on Cycle 1 Day 1 $\geq 2700 \text{ mg/m}^2$
- 2400 mg/m^2 if $2100 \text{ mg/m}^2 \leq$ the calculated dose level on Cycle 1 Day 1 $< 2700 \text{ mg/m}^2$
- 1800 mg/m^2 if $1500 \text{ mg/m}^2 \leq$ the calculated dose level on Cycle 1 Day 1 $< 2100 \text{ mg/m}^2$

Etoposide:

- 100 mg/m² if the calculated dose level on Cycle 1 Day 1 \geq 90 mg/m²
- 80 mg/m² if 70 mg/m² \leq the calculated dose level on Cycle 1 Day 1 < 90 mg/m²
- 60 mg/m² if 50 mg/m² \leq the calculated dose level on Cycle 1 Day 1 < 70 mg/m²

For subjects in expansion cohorts (2A, 2B and 3B), the actual dose level will be set to the planned dose level regardless of capped dose.

The planned dose level is used in the Full Analysis Set and Per Protocol Analysis Set, while the actual dose level (BSA-adjusted dose level) will be used for the Safety Analysis Set, PK Analysis Set, and DLT Analysis Set. Regarding summarization of mean and mean change from Baseline for laboratory, vital sign, and ECG data, if 2 or fewer subjects in each of the treatment groups have data for a given cycle, the applicable cycle(s) will not be summarized and the table will be curtailed. For example, if at Cycle 12 the 3 treatment groups have 4, 3 and 1 subjects, respectively, then Cycle 12 will be summarized for all treatment groups. If at Cycle 13, the 3 treatment groups have 2, 2 and 1 subject, respectively, and at subsequent cycles no treatment has 3 or more subjects, then the table will not be produced for Cycle 13 and all subsequent cycles. However, for shift tables and other analyses of worst postbaseline values, all data will be included.

5.4 Primary, Secondary and Exploratory Analyses

5.4.1 Primary Dose-Finding Analyses

5.4.1.1 Cohort 1: (Single-Agent Dose-Finding)

Cohort 1, the lenvatinib single-agent dose-finding group, will enroll up to 24 subjects. A TiTE-CRM design will be used to determine the RD of lenvatinib and to increase the flexibility by allowing continuous accrual with no trial suspensions, which are typically needed when the toxicity assessment of subjects previously recruited is not completed (Smith, et al., 1998; Cheung, 2009). Using this TiTE-CRM design, an eligible subject can be included in the trial at any time, without waiting for the completion of prior subjects (Doussau, et al, 2012). The model will be re-estimated considering all the toxicity observations currently available. The subject will be treated at the best current estimate of the RD. Individual subjects on long-term treatment may be treated at a dose below the dose recommended by the model for safety reasons.

A 1-parameter empirical power model will be used to assess the relation between the dose level and the probability of DLT:

$$F(d, \alpha) = P_d^{\exp(\alpha)}$$

where $F(d, \alpha)$ is the estimated probability of DLT at dose-level d , P_d is the prior probability of DLT at dose level d , and α is the unknown parameter to be estimated by the model.

The vector $\{p_{0d}\}$ represents the initial guesses of toxicity probabilities, reflecting the clinicians' prior impression. The skeleton of initial guesses of toxicity probabilities $\{p_{0d}\}$ is numerically calibrated using the approach of [Lee et al. \(2005\)](#) and [Cheung \(2009\)](#) and using the “*getprior*” function of R, ensuring good design operating characteristics. Based on consultation with the clinicians, the delta (half of the width of the CI) defining the indifference interval was set at 0.06 (indifference interval: 0.14 to 0.26) and the prior maximum tolerated dose (MTD₀) at Dose 2 (14 mg/m²) is likely to be the RD (same as in adults). This yields a vector of prior probabilities $\{p_{0k}\}$ equal to 0.03, 0.10, 0.20, and 0.33, for the doses 9 mg/m², 11 mg/m², 14 mg/m², and 17 mg/m², respectively, that was found reasonable by the clinicians. A noninformative prior distribution Normal (0, 1.34) has been assigned for α in the Bayesian computation.

The simulation study confirmed that the operating characteristics of the model defined with these parameters were reasonable, with more than 50% correct selection of the RD in 3 contrasted scenarios. Starting with Dose 1, the prior distribution of the parameter α will be updated by the accruing data on DLTs each time a subject completes evaluation for toxicity in Cycle 1.

5.4.1.2 Cohort 3A: Osteosarcoma Combination Dose-Finding

The DLT will be assessed to determine the RD of lenvatinib in combination with ifosfamide and etoposide. DLTs occurring during Cycle 1 will be evaluated and the subjects will be assigned a dose based on the rules for dose escalation and de-escalation (see [Section 3.3.4.3](#)). The RD of lenvatinib in combination with ifosfamide and etoposide will be used to treat osteosarcoma subjects in Cohort 3B.

5.4.2 Efficacy Analyses

The tumor response data used in the primary analyses of the PFS-4 rate and ORR will be obtained from the investigator's assessment of the imaging scans. No independent tumor assessments will be performed as part of this study. Tumor response will be assessed by RECIST 1.1. All the efficacy analyses will be performed on the Full Analysis Set, and the Per Protocol Analysis Set for all tumor response-related efficacy endpoints. A tabular summary of key features of the efficacy analyses is described in SAP [Appendix 13.2 \(Summary of Efficacy Analyses\)](#).

5.4.2.1 Primary Efficacy Analyses

COHORT 2A: DTC

The primary efficacy endpoint is ORR for subjects with measurable disease and BOR for all subjects. Tumor response will be based on RECIST 1.1 and assessed every 8 weeks. The analysis will be descriptively performed on the Full Analysis Set.

COHORT 2B: SINGLE-AGENT EXPANSION

The primary efficacy endpoint is the PFS-4 rate based on RECIST 1.1. This is the proportion of subjects free of progression at 4 months. The PFS-4 rate will be estimated using the binomial proportion and the corresponding 80% and 95% exact binomial distribution CIs ([Clopper and Pearson, 1934](#)) will also be provided. The PFS-4 rate will also be tested using a null hypothesis that the PFS-4 rate is $\leq 25\%$ tested against the alternative hypothesis of a PFS-4 rate $\geq 45\%$, using the 1-sample exact test of a single proportion, at the 1-sided 0.1 level. These analyses will be performed on the lenvatinib-naïve subjects in the Full Analysis Set and the Per Protocol Analysis Set.

The PFS-4 rate will be calculated using PFS-4 evaluable subjects. These are defined as follows.

PFS-4 evaluable subjects:

- includes subjects who were treated with study medication at least 16 weeks;
- includes subjects who died or radiologically progressed within 16 weeks after the first administration of study medication. These subjects are not considered free of progression at 4 months;
- includes subjects who received anticancer treatment within 16 weeks after the first administration of study medication. These subjects are not considered free of progression at 4 months;
- excludes those who discontinue the study due to AE or reasons other than disease progression, death, or receiving anticancer treatment within 16 weeks after the first administration of study medication;
- excludes subjects administered any study medication with no baseline or no postbaseline tumor assessments.

COHORT 3B: OSTEOSARCOMA COMBINATION EXPANSION

The primary efficacy endpoint is the PFS-4 rate based on RECIST 1.1. This is the proportion of subjects free of progression free at 4 months. The PFS-4 rate will be estimated using the binomial proportion along with the corresponding exact binomial 80% and 95% CIs. The PFS-4 rate will be tested using a null hypothesis that PFS-4 rate is $\leq 25\%$ tested against the alternative hypothesis of a PFS-4 rate $\geq 50\%$, using the 1-sample exact test of a single proportion, at the 1-sided 0.1 level. This analysis will be performed on the lenvatinib-naïve subjects in Full Analysis Set and Per Protocol Analysis Set, while subjects enrolled from Cohorts 1 and 2B will be summarized only as appropriate.

The PFS-4 rate will be analyzed using PFS-4 evaluable subjects. These are defined as follows.

PFS-4 evaluable subjects:

- includes subjects who were treated with study medication at least 18 weeks
- includes subjects who died or radiologically progressed within 18 weeks after the first administration of study medication. These subjects are not considered free of progression at 4 months.
- includes subjects who received anticancer treatment within 18 weeks after the first administration of study medication. These subjects are not considered free of progression at 4 months.
- excludes those who discontinue the study due to AE or other reasons than disease progression, death , or receiving anticancer treatment within 18 weeks after the first administration of study medication
- excludes subjects administered any study medication but had no baseline or no postbaseline tumor assessments.

SURGICALLY REMOVED LESIONS

For Cohorts 2B, 3A and 3B, removal of existing (not new) osteosarcoma metastatic lesion(s) is permitted after the completion of the first 4 months of the treatment period without PD. The time points for tumor response assessment after tumor removal will be considered ‘Not Evaluable’ unless the tumor response is considered PD for the following reasons:

- appearance of an unequivocal new lesion
- unequivocal progression of non-target lesions or target lesions

Lesions removed before the first 4 months are permitted only in the case of PD.

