9.7.1.1 Study Endpoints

PRIMARY ENDPOINT(S)

Cohort 1 (Single-Agent Dose-Finding)

- RD based on the TiTE-CRM design.

Cohort 2 (Single-Agent Expansion)

- Cohort 2A: DTC Group: ORR (CR + PR) for subjects with measurable disease and BOR for all subjects based on RECIST 1.1
- Cohort 2B: Osteosarcoma Group: PFS-4, ie, the percentage of subjects who are alive and free of disease progression 4 months after the first dose based on RECIST 1.1

Cohort 3A (Combination Dose-Finding)

- RD of the combination treatment (lenvatinib + ifosfamide + etoposide)

Cohort 3B (Combination Expansion)

- PFS-4, ie, the percentage of subjects who are alive and free of disease progression 4 months after the first dose based on RECIST 1.1

SECONDARY ENDPOINTS

Cohort 1 (Single-Agent Dose-Finding)

- Efficacy
 - BOR over the treatment period

- ORR
- DOR
- Disease Control Rate (DCR) defined as the percentage of subjects with measurable disease who have a BOR of CR or PR or stable disease (SD) or subjects with evaluable disease who have a BOR of CR or Non-CR/Non-PD. To be assigned a best overall response of SD or Non-CR/Non-PD, the time from the first administration of study drug until the date of documented SD or Non-CR/Non-PD should be ≥ 7 weeks.
- Clinical Benefit Rate (CBR) defined as the percentage of subjects with measurable disease who have a BOR of CR or PR or durable SD lasting ≥ 23 weeks or subjects with evaluable disease who have a BOR of CR or durable Non-CR/Non-PD lasting ≥ 23 weeks
- PFS defined as the time from the date of the first administration of study drug to the date of first documentation of disease progression or date of death, whichever occurs first
- TTP defined as the time from the date of the first administration of study drug until the date of first documentation of disease progression
- OS defined as the time from the date of the first administration of study drug until the date of death from any cause. Subjects who are lost to follow-up and those who are alive at the date of data cutoff will be censored at the date the subject was last known to be alive (or the data cutoff date).
- Safety
 - AEs, SAEs, clinical laboratory values, vital signs, 12-lead ECG, urine dipstick, occult blood in stool, Lansky play scores or Karnofsky performance scores, physical examination findings, and height and closure of proximal tibial plates during treatment and follow-up
- Plasma lenvatinib exposure parameters

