5.1 Study Endpoints

5.1.1 Primary Endpoints

For Cohort 1, the primary endpoint is RD of lenvatinib based on the TiTE-CRM design. While for Cohort 3A, it is RD of the combination treatment (lenvatinib + etoposide + ifosfamide).

For the three Phase 2 cohorts, the primary endpoints are:

- Cohort 2A (DTC): ORR, ie, the proportion of subjects who have a BOR of complete response (CR) or partial response (PR) for subjects with measurable disease and BOR for all subjects based on RECIST 1.1
- Cohort 2B (Osteosarcoma): PFS-4, ie, the percentage of subjects evaluable for PFS-4 who are alive and without PD at 4 months from the first dose based on RECIST 1.1. Subjects evaluable for PFS-4 includes those treated at least 4 months or those who died or radiologically progressed within 4 months after first dose.
- Cohort 3B: PFS-4

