8.3.2 Date/Time Definitions

The following factors will be used to convert days to months or years:

1 month = 30.4375 days

- Time from first diagnosis to first dose (months) is:
(Date of first dose – Date of first diagnosis) / 30.4375
- Time from first metastatic diagnosis to first dose (months) is:
(Date of first dose – Date of first metastatic diagnosis) / 30.4375
- Time from last medication to first dose (months) is:
(Date of first dose – End date of last medication) / 30.4375
- Time from last procedure to first dose (months) is:
(Date of first dose – Start date of the last anti-cancer procedure) / 30.4375
- Time from last radiotherapy to first dose (months) is:
(Date of first dose – End date of the last radiotherapy) / 30.4375
- Time from last radioiodine therapy to first dose (months) is:
(Date of first dose – End date of the last radioiodine therapy) / 30.4375

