13.2 Summary of Efficacy Analyses

Efficacy Variable	Analysis Set	Statistical Method	Tumor Assessments
PFS-4	Full Analysis Set, Per Protocol Analysis Set	Number (percent) of subjects who are alive, free of disease progression, and did not receive anticancer medication 4 months after the first dose, and its exact 80 and 95% CIs using method of Clopper and Pearson.	Investigator
		Cohort 2B: PFS-4 rate will be tested using a Null hypothesis that PFS-4 is $\leq 25\%$ tested against the alternative hypothesis of a PFS-4 $\geq 45\%$, using the 1-sample exact test of a single proportion, at the 1-sided 0.1 level.	
ORR	Full Analysis Set, Per Protocol Analysis Set	Cohort 3B: PFS-4 rate will be tested using a Null hypothesis that PFS-4 is $\leq 25\%$ tested against the alternative hypothesis of a PFS-4 $\geq 50\%$, using the 1-sample exact test of a single proportion, at the 1-sided 0.1 level.	Investigator
PFS	Full Analysis Set, Per Protocol Analysis Set	Number (percent) of subjects (with PR + CR) and its exact 95% CI using method of Clopper and Pearson.	Investigator
OS	Full Analysis Set	KM method: Median, Q1, and Q2 PFS will be presented, with 2-sided 95% CIs (Brookmeyer and Crowley). Cumulative probability of PFS at 4 and 12 months will be presented with 2-sided 80 and 95% CIs (Greenwood using the log-log). KM plot will also be provided.	Not Applicable

Efficacy Variable	Analysis Set	Statistical Method	Tumor Assessments	
		plot will also be provided.		
BOR	Full Analysis Set, Per Protocol Analysis Set	Number (percent) and 95% exact CIs will be provided for each BOR category	Investigator	
DOR	Full Analysis Set, Per Protocol Analysis Set	KM method: Median, Q1, and Q2 PFS will be presented, with 2-sided 95% CIs (Brookmeyer and Crowley).	Investigator	
TTP	Full Analysis Set, Per Protocol Analysis Set	Kaplan-Meier method: Median, Q1, and Q2 TTP will be presented with 2-sided 95% CIs (Brookmeyer and Crowley). Cumulative probability of TTP at 4 and 12 months will be presented with 2-sided 80 and 95% CIs (Greenwood using log-log). Kaplan-Meier plot will also be provided.	Investigator	

Efficacy Variable	Analysis Set	Statistical Method	Tumor Assessments
DCR	Full Analysis Set	Number (percent) of subjects (measurable disease with CR + PR + stable disease [SD] \geq 7 weeks, evaluable disease with CR + Non-CR/Non-PD \geq 7 weeks) and its exact 95% CI using method of Clopper and Pearson.	Investigator

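### For its primary endpoint PFS-4 the SAP gives two unreconciled windows in each osteosarcoma expansion cohort: 4 months against 16 weeks (2B) or 18 weeks (3B)

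*SAP*

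**What the plan says.** The protocol (9.7.1.1) defines PFS-4 as "the percentage of subjects who are alive and free of disease progression 4 months after the first dose based on RECIST 1.1", for both Cohort 2B and Cohort 3B. It gives no count of days or weeks.

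The SAP then states the window in two ways:

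- **In months.** SAP 5.1.1, under Cohort 2B, says: "Subjects evaluable for PFS-4 includes those treated at least 4 months or those who died or radiologically progressed within 4 months after first dose". Its Cohort 3B bullet only names the endpoint. The summary table in SAP 13.2 covers both cohorts and counts subjects who are "alive, free of disease progression, and did not receive anticancer medication 4 months after the first dose".
- **In weeks.** For Cohort 2B, SAP 5.4.2.1 says that the evaluable set "includes subjects who were treated with study medication at least 16 weeks" and "includes subjects who died or radiologically progressed within 16 weeks after the first administration of study medication"; the latter are failures. For Cohort 3B the same section says "includes subjects who were treated with study medication at least 18 weeks" and "includes subjects who died or radiologically progressed within 18 weeks after the first administration of study medication". SAP 5.4.3.1 sends the exploratory Cohort 3A analysis to the 3B rule.

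The only month length in the SAP is in 8.3.2: "1 month = 30.4375 days". The uses listed there are baseline intervals, such as time from diagnosis to first dose. SAP Section 7, which lists departures from the protocol's analyses, does not mention the PFS-4 window.

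**The concern.** Sixteen weeks is shorter than 4 months and eighteen weeks is longer. Within a cohort, a subject whose progression, death, new therapy or treatment stop falls between the two limits is therefore scored differently by two sections of the same SAP. The affected endpoint is primary, is assessed by the investigator in an open-label study, and feeds a small integer decision rule: in 2B at least 5 of 15, then at least 10 of 27.

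The 2B week rule also has a direction. Its failure window closes on the last day of the scheduled Week-16 scan. If that scan is taken late and shows progression, 5.4.2.1 as written scores the subject as a success. Delay can therefore only help the drug.

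**Working it through.** **1. The limits in days**

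- 16 weeks: 16 × 7 = 112.
- 18 weeks: 18 × 7 = 126.
- 4 months, if the 8.3.2 factor is applied: 4 × 30.4375 = 121.75. This is inferred; the SAP does not print it for PFS-4.
- Gaps: 121.75 − 112 = 9.75 days in 2B, and 126 − 121.75 = 4.25 days in 3B.

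**2. Where the scheduled scans fall**

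SAP 8.1 places scans within Week 8 of each 8-week interval (2B) and within Week 6 of each 6-week interval (3A, 3B). The Week-16 scan then spans days 106 to 112 and the Week-18 scan days 120 to 126.

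- In 2B an on-schedule scan falls inside both limits and creates no conflict. A conflict needs a late or unscheduled scan, a death, new therapy or a treatment stop on about days 113 to 121.
- In 3B five of the seven on-schedule days (122 to 126) lie beyond 121.75. No deviation is needed.

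**3. The same subject under both rules**

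| Subject | SAP 5.4.2.1 (weeks) | 4-month rule |
|---|---|---|
| 2B, progression on day 115 | success | failure |
| 2B, stops for an adverse event on day 116, no progression | evaluable success | not evaluable |
| 3B, progression on day 124 | failure | success |
| 3B, stops for an adverse event on day 123, no progression | excluded | evaluable success |

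The last row carries the evaluability wording of 5.1.1 over to 3B.

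**4. The plan's own 2B figure**

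Inputs (SAP Section 4): null rate 25%, alternative 45%, 15 then 27 evaluable subjects, continue at 5 or more, active at 10 or more. The probability of declaring activity at rate p is the sum of b(x; 15, p) × b(y; 12, p) over x ≥ 5 and x + y ≥ 10.

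- p = 0.25 gives 0.097, within the stated 0.10.
- p = 0.45 gives 0.801, matching the stated 80%.

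The design reproduces.

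**5. Illustration for late Week-16 scans in 2B**

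Assume constant hazard, progression found at the Week-8 and Week-16 scans, and the design rate holding at day 112. Then S(56) = √S(112), and the expected number of progressions first seen at Week 16 is 27 × S(56) × (1 − S(56)).

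- At 45%: 27 × 0.671 × 0.329 = 6.0.
- At 25%: 27 × 0.5 × 0.5 = 6.75.

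Suppose 10 to 30% of those scans are late and the subjects are still on treatment. Misclassified successes are 0.6 to 1.8 at 45% and 0.7 to 2.0 at 25%. Under the null the apparent rate becomes 0.25 + 0.1 × 0.25 = 0.275, up to 0.25 + 0.3 × 0.25 = 0.325. The formula in step 4 then gives a type I error of 0.160 and 0.333, against 0.097.

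**6. A second assumption as a check**

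Let PFS be exponential, with the design rates holding at 121.75 days and events dated when they occur.

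- 2B read at 112 days: 0.25^(112/121.75) = 0.279 and 0.45^(112/121.75) = 0.480. The type I error is 0.172 and power 0.871. About 27 × 0.029 = 0.8 subjects fall in the gap.
- 3B read at 126 days: 0.25^(126/121.75) = 0.238 and 0.50^(126/121.75) = 0.488. About 15 × 0.012 = 0.2 subjects fall in the gap.

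In 2B the shift would be smaller if events surface only at on-schedule scans. In 3B the count would then depend on how many Week-18 scans land on days 122 to 126, which the documents do not say.

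**The case against.** The strongest reply is that 5.1.1 is a general statement and 5.4.2.1 its operational form. Section 5.4.2.1 itself ties progression within 16 or 18 weeks to not being progression-free at 4 months. The week counts match the scan schedules, SAP 5.4.2.2 repeats them by cohort, and Protocol 9.7.1 leaves further detail to the SAP. This makes the week rule the likelier intention. It does not settle the matter: 5.1.1 also states an operational evaluability rule, in months, and no section is given precedence. Following 5.4.2.1 alone still leaves the late-scan bias in 2B.

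Several limits on the point stand:

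- The day ranges rest on the 8.3.2 factor, whose listed uses are baseline intervals only.
- The boundary may shift by a day. SAP 5.6 makes the first-dose date Study Day 1 (for safety analyses), so 112 elapsed days is Study Day 113, and a scan one day late might still count as within 16 weeks.
- The 10 to 30% late-scan range has no source in the documents.
- Any integer cut-off can turn on one subject, so that alone shows no defect.

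A reader might also infer that 16 weeks, 18 weeks and 4 months all compete for the same subject. They do not. The two week counts sit under separate cohort headings, and a 2B subject who later enters 3B is not lenvatinib-naïve and so is outside the 3B primary analysis.

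**Conclusion.** Wrong as written. Within each cohort two sections define the primary endpoint's window differently, and subjects exist whom the two rules score in opposite ways. In 2B the week rule favours the drug when the Week-16 scan is late; in 3B the week rule is the stricter one.

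The size is uncertain. In 2B it is about 0.6 to 2.0 of 27 subjects, with a type I error of about 0.16 to 0.33 instead of 0.097, if hazard is constant and 10 to 30% of Week-16 progression scans are late. The exponential check gives 0.172. In 3B the same check puts about 0.2 of 15 subjects in the gap.

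Two stronger readings are not supported. The first is that ordinary 2B scans are misclassified: on-schedule scans end by day 112 and agree under both rules. The second is that one extra success doubles the 2B false-positive risk, from 0.113 at 10 of 27 to 0.214 at 9 of 27. Those are single-stage tails; under the planned two-stage rule, with 5 of 15 held fixed, the values are 0.097 and 0.164.

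**What to change.** State that the PFS-4 landmark is the scheduled Week-16 scan in 2B and the scheduled Week-18 scan in 3A and 3B. Give each cohort one explicit day count, say whether the first-dose date is day 0 or day 1, and set one scan window.

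A window of up to 7 days late, for example, accepts the landmark scan to day 112 + 7 = 119 in 2B and 126 + 7 = 133 in 3A and 3B. Progression on the landmark scan within that window is a failure, whatever its day. A scan taken later is not the landmark scan, and the SAP should say how such a subject is handled. The 7 days is a choice, and it moves 3B further from a calendar 4 months; what matters is that it is fixed in advance.

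Use this definition in SAP 5.1.1, 5.4.2.1 and 13.2. Section 5.4.3.1 already points to the 3B rule and needs no separate edit. Add a line in Section 7 saying that this makes the protocol's 4 months operational.

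The cost is SAP wording before database lock. The downside is that a few late-scan successes become failures.
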